5.03. Frequency of analyses

The randomisation code will be broken after the ninth study visit has been completed in all clusters (24 months after the last cluster was included in the study) and the database has been reviewed for data accuracy. The main analysis will be done at this point. The analysis will first be completed using letter-coded intervention names (A, B, C). Once the principal investigators have reviewed the analysis results and agreed that there is no need for further data or analysis edits, the code linking specific interventions to the letter codes will be opened.

As described in chapter 4.13, one interim efficacy analysis will be completed when 60% of the planned post-MDA 3-month intervals have been completed. If there is a statistically significant mortality difference between both of the azithromycin groups and the placebo group but not between the two azithromycin groups, the placebo arm will be discontinued, and trial completed with two arms only. If there is also a statistically significant difference between the two azithromycin groups, the trial will be stopped, and the team will offer to work with Malian Ministry of Health to provide azithromycin MDA in the trial site and two other regions of Mali.

Concomitantly with the interim efficacy analysis, there will be an interim safety analysis.

Additional safety or efficacy analyses will be completed if requested by the study DSMB.

The relative risk reduction (RRR) of 20% in the azi-biannual group is modelled on the MORDOR-trial, in which the point-estimate for mortality reduction among under-one-year old infants was 25% (in all the study countries) (Keenan et al, 2018). We estimate this reduction be slightly lower in Mali, because of the seasonal malaria chemoprevention that will be offered to 3-11-month-old infants in the Mali but was not practiced at the MORDOR sites. The 40% RRR for the azi-quarterly group is also modelled on MORDOR result indicating that in that sample practically all the mortality effect was concentrated in the first 3 months after the MDA (Porco et al, 2019).

For the AMR data collection, the sample size will be 60 clusters or 1,350 children per time-point. This number will be tested from 4–14-month-old children at 12 months after the intervention has stopped and from 49–59-month-old children when 8 rounds of MDA have been completed. At the three other time points, we will test 450 children (taken

randomly from 20 clusters / arm). In total, this will mean 5,400 AMR-analyses for *S. pneumoniae* and the same number for *E. coli*.

The AMR sub-sample size is based on the following assumptions

1. 95% *E. coli* and 65% *S. pneumoniae* recovery rate from the collected samples
2. AMR prevalence of 12% in the control group for *E. coli* and 6% for *S. pneumoniae*. These figures come from analysis of azithromycin resistance in 50 *E. coli* and 50 *S. pneumoniae* samples from Mali in the so called ABCD trial.
3. Non-inferiority margin of 10%-points in AMR prevalence
4. 80% power, one-sided 2.5% type 1 error rate for each pairwise comparison against placebo control
5. Coefficient of variation of 0.3 in AMR among clusters.

For the analyses on azithromycin mechanism, we are using a convenience sample, i.e. all available children in the intended age-brackets (and avoiding repeated venous blood collection from the same children), in the study clusters where the AMR work is done. The sample size of 1,000 – 1,350 / analysis, or a mean of 333 - 450 / intervention arm, will provide these analyses 80% power at 5% two-sided type 1 error rate to detect an effect size of 0.25 – 0.30, assuming an intra-cluster correlation coefficient of 0.03 and a design effect of 1.6 to 2.

For intra-household analyses there are no pre-set hypotheses, but the data will be used for descriptive purposes.

5.05. Subgroup analyses

For hypothesis generating purposes, we plan to carry out exploratory tests for interaction between the MDA intervention and the selected baseline variables, using the mortality and growth outcomes. Tests of hypotheses concerning intervention effects in these subgroups will be performed only if the interaction tests give statistically significant results ($p<0.1$).

The following variables would be assessed potential effect modifiers

1. Infant age at the time of MDA (1-5 months vs 6-11 months)
2. Infant weight-for-age, length-for-age, weight-for-length at the time of MDA
3. Infant sex
4. Season of MDA dosing (malaria versus non malaria season) and SMC implementation in village (SMC given versus SMC not given)
5. Cluster level coverage of SMC
6. Cluster level baseline mortality (established at first census)
7. Cluster and individual level coverage and number of administered azithromycin MDA doses
8. District of residence
9. Distance from the nearest health facility
10. Household asset or income index
11. Household WASH index
12. National outreach strategy category (standard/advanced)

13. Hard-to-reach village status assessed by the field workers

6. Ethical considerations

6.01. General principles

The trial will be performed according to Good Clinical Practice guidelines (ICH-GCP) and it will adhere to the principles of Helsinki declaration and regulatory guidelines in Mali. Trial recruitment shall not begin before the ethics committee in Mali (Comité D'Ethique de l'USTTB (Université des Sciences, des Techniques et des Technologies de Bamako) has given a favourable statement on it. An ethics committee in Finland has no legal mandate to authorize trials abroad, but a favourable opinion from one (Pirkanmaan Sairaankoitoiin eettinen toimikunta) will be required for TAU researchers to participate in the project.

6.02. Informed consent

Permissions for trial implementation will be sought on three levels at the study site: Village (cluster), household, and individual child.

For village enrollment, members of the study team will visit village leadership, give them oral and written information about the trial (Appendix 1a) and request a permission to make an information campaign and perform study activities in the selected village. The response will be given verbally and documented electronically in a study database (Appendix 1b).

If a village level permission is granted, the study team will run an information campaign about the upcoming trial in the village and its nearby health facilities. After one week of general information campaign, the team will start household visits.

A team consisting of a community volunteer and a study team member will conduct the household visits. At each household visit, the team members will inform the heads of household and other household members about the purpose and processes of the trial, provide a written documentation about it (Appendix 2a) and request a consent (Appendix 2b) to visit the household and collect trial data on a total of nine times over a period of two years. The response will be given verbally and documented electronically in a study database. If the person giving consent is illiterate, study personnel will ask her / him to invite an impartial witness to verify the consent. The name and home village of the impartial witness will be recorded in the consent database.

Since the local language (Bambara) is mostly not a written language, many people may not be able to read it. For standardisation purposes, the team will write and hand out the participant information and consent form texts both in French and in Bambara. From the

Bambara text, the trial team will make an audiotape, so that the message can be given in a standardised manner by different data collectors. For information purposes, the team will also make a picture booklet as well as Bambara language videos describing the study procedures.

During the household visits, the community volunteer and the data collector request a permission to weight and provide study drugs to all 1-11- month-old children (age 29-364 days). Information about the purpose and process for this treatment is provided verbally and the response is also provided verbally and documented electronically in a study database (Appendix 3).

At selected visits, sub-samples of children are invited for further data collection on secondary outcomes and other relevant data at a nearby health center or at central location in a village. Participant information and consent forms for the secondary outcome data collection are shown as Appendices 4a (participant information) and 4b (consent form).

6.03. Possible risks and benefits to study participants

Azithromycin stimulates smooth muscle contraction and may cause mild abdominal discomfort, vomiting, or diarrhea in some children. In earlier MDA trials with single-dose azithromycin use in infants, this has not been frequently reported by caregivers (Porco et al., 2009; Keenan et al., 2018; Chandramohan et al., 2019). In several studies, where azithromycin treatment has been compared to other antibiotics, the incidence of gastrointestinal side-effects has been smaller in the azithromycin than the comparison groups (Roord et al., 1996; Ferwerda et all., 2001; Langly at al., 2004). Hence, we don't expect much of this problem for LAKANA participants.

Among newborns, there is one theoretical safety concern, because of which neonates will be excluded from study drug administration in the LAKANA trial. In this age group, azithromycin may induce pyloric stenosis, an obstruction of gastric outlet that may require surgical intervention. In some population analyses, an increased risk for this rare condition has been associated with azithromycin use among under-14-day-old neonates, but not older children (Eberly et al., 2015). Since it is not known if the increased pyloric stenosis risk has been eliminated by one month of post-natal age also among preterm babies and since we will not be able to ascertain the duration of pregnancy at birth, all infants whose weight is below 3.0 kg will be excluded from the trial (3.0 kg is the 3rd weight centile among healthy 1 month olds, according to WHO growth charts).

Besides the possibly increased risk of the rare pyloric stenosis in newborns and possibly causing abdominal discomfort, azithromycin has an excellent safety profile and is not expected to pose health risks to LAKANA participants. In the United States, azithromycin has been FDA approved for use only for children who are six-months or older, but there are numerous scientific reports and a systematic review that document safety also for younger infants (Pinto et al., 2012; McCallum et al., 2013; Beigelman et al., 2015; Smith et al., 2015). There are also several official US guidelines that recommend azithromycin use for under-six month old infants (American Academy of

Pediatrics, 2012; Centers for Disease Control, 2019). Also, in trachoma control programs, azithromycin has been used for post-neonatal infants for 20 years without safety concerns.

All participants will benefit from trial participation in terms of repeated home visits, during which caregivers may ask health-related questions from the study personnel. The study staff making home visits will not be medically trained and they will be instructed not to provide direct medical advice. However, if needed, they will facilitate referral to a local health facility. If a further referral to a hospital is required, the study team will assist in transfer where necessary. For children participating in the mechanistic substudy for whom blood samples are collected and Hb and CRP levels measured on site: on the first visit, if a child is asymptomatic or has mild respiratory symptoms, and the CRP is above or Hb is below a critical threshold based on reference ranges from the Mali national and local guidelines in use at that time, the child will be given the study drug and then actively referred to the nearest health clinic. Transportation will be ensured. On the second visit two weeks later, if the Hb reaches a critical threshold based on reference ranges from the Mali national and local guidelines in use at that time, the child will be actively referred to the nearest health clinic and transportation will be ensured. Upon referral, a paper copy of an instruction leaflet to health clinics will be given to the caregiver to show at the clinic (Appendix 5).

Two thirds of the participants will receive azithromycin MDA, which is expected to reduce mortality and offer other health benefits to the participants. At the end of the trial, if the analysis suggests a mortality reduction by azithromycin, all participants who are 1-11 months (29-364 days) old, will receive 20 mg / kg azithromycin.

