We will test the first three of the above-described hypotheses (about malaria elimination and reduction of general or intestinal inflammation) from the first group of children, i.e., 4–11-month-old infants living in communities receiving their 4th MDA. From these infants, a study nurse will collect a heel-prick blood sample and a flocculated rectal swab before they have received any MDA. They will collect another heel prick blood sample and a stool sample (or rectal swab if stool collection fails) two weeks after the 4th round of MDA has been conducted in their communities. From the collected blood, the nurse will measure hemoglobin and CRP concentration with an on-site reader and store blood on a filter paper for later malaria diagnostics with DNA-amplification. From the stool sample, a laboratory technician will determine calprotectin and alpha-1-antitrypsin concentrations with commercially available ELISA tests. Additional stool and urine samples will be collected and stored for later analyses (on hypotheses 5-7). In the analysis phase, we will compare prevalence of malaria parasitemia, mean blood hemoglobin and CRP concentration and mean fecal neopterin, myeloperoxidase, and alpha-1-antitrypsin concentration in the three study arms, both before and after the first MDA treatment.

From the second and third group of children (12–14-month-olds who have received 3-4 doses of MDA and 6–8-month-olds who have received 2-3 doses of MDA) we will test hypotheses 2-4, i.e., those about broader general and intestinal inflammation and immune function and development. These infants will be invited to a health facility or a central location in a village - after the MDA visit to their household. At the clinic, a study nurse will receive a home collected stool sample or take a rectal swab if stool collection has failed. S/he will also draw a 5 ml blood sample and collect a 10 ml

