The age groups have been selected in a way that there will be no more than one venous blood sample per child during the study. From the 6-8-month of children, we will primarily assess immune development and vaccine responses to tetanus and rotaviral vaccines (given before the age of 6 months). From the 12-14-month of children, we will assess immune development and vaccine response to measles vaccine (given usually between 9 and 12 months of age). From both age-groups, we will also assess malaria prevalence by a DNA amplification test. Immune development and infection are best studied among over-6-month-old children, since by this age infants will have lost most of their passive maternal immunity and will be increasingly susceptible for infection, inflammation, dysbiosis, and EED.

Figure 7 summarises analyses planned to be completed in the first phase.

Study question	Biological specimen	Laboratory analysis	Child age	Level of analysis	Timing of lab sample vs MDA	# of given MDA doses	# of children
Malaria clearance	Blood (dried)	P. falciparum DNA amplification	4-11 mo	Individual	Paired (before and 14 d after)	1	1000
Consequence of malaria clearance	Blood (fresh)	Hemoglobin concentration	4-11 mo	Individual	Paired (before and 14 d after)	1	1000
Reduction of systemic inflammation	Blood (fresh)	CRP concentration	4-11 mo	Individual	Paired (before and 14 d after)	1	1000
Reduction of intestinal inflammation	Stool	Calprotectin concentration	4-11 mo	Individual	Paired (before and 14 d after)	1	1000

Figure 8 summarises biological samples planned to be stored from the study participants (in addition to those, stored in the AMR part of the study). These samples will be used address hypotheses 5-7 of the mechanistic studies as well as for any additional hypotheses formulated during the trial. If all samples were collected and aliquoted as planned, there would be a total of 51,800 stored vials, i.e., these samples will fill one -80°C freezer.

Biological specimen	Child age	MDA or study visit	Timing of lab sample vs MDA	# of given MDA doses	Storage media	Estimated # of aliquots	Volume / aliquot	Storage temperature	# of children
Blood	4-11 mo	4	Before	1-3	Filter paper	2	50 ul	-80°	1000
Stool	4-11 mo	4	Before	1-3	Cryovial	4	1.5 g	-80°	1000
Urine	4-11 mo	4	Before	1-3	Cryovial	3	1.5 ml	-80°	1000
Blood	4-11 mo	4	14 d after	1-3	Filter paper	2	50 ul	-80°	1000
Stool	4-11 mo	4	14 d after	1-3	Cryovial	4	1.5 g	-80°	1000
Urine	4-11 mo	4	14 d after	1-3	Cryovial	3	1.5 ml	-80°	1000

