For growth analysis, we will calculate anthropometric indices LAZ (length for age Z-score), WAZ (weight for age Z-score), WLZ (weight for length Z-score), and MUAC-Z (mid upper arm Z-score) for each participant as described in chapter 4.10. We will then calculate mean (SD) group values for each variable. In analyzing differences between groups, controlling for multiplicity will be conducted as per the closed-testing procedure,

by testing a global null hypothesis at 5% significance level. If the global null hypothesis is rejected ($p<0.05$), three pairwise comparisons will be carried out. The differences between the three groups and their 95% CIs will be obtained from mixed-effects regression models, that account for the clustering of observations. The global p-value will also be obtained from these models.

For mechanism of action analyses, we will calculate the prevalence of malaria parasitemia as well as mean plasma CRP, blood hemoglobin and other biomarker concentration before and at two weeks after the MDA. We will then test a global hypothesis about differences between the groups using mixed-effects models, which account for clustering, for continuous variables and proportions, respectively with different, suitable link functions. If the global test shows a statistically significant difference ($p<0.05$) between the three groups, we will proceed into three pair-wise comparisons, providing the difference (95% CI) in means or proportions. If the p-value obtained from mixed-effects models is <0.05 , the results will be considered supportive of the trial hypothesis.

All children will be analysed in the group into which they were initially randomized, i.e. on an intention-to-treat basis.

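### Section 6.03 refers infants for raised CRP or low Hb at the first mechanistic-study visit but for Hb alone two weeks later, although CRP is read on site both times

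*Combined protocol and SAP*

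**What the plan says.** Section 6.03 gives the referral rules for infants in the mechanistic sub-study whose Hb and CRP are measured in the field.

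- **First visit.** The rule covers a child who has no symptoms or only mild respiratory ones, "and the CRP is above or Hb is below a critical threshold". That child receives the study drug and is then actively referred, with transport.
- **Second visit.** The sentence begins "On the second visit two weeks later, if the Hb reaches a critical threshold" and again provides active referral with transport. It does not mention CRP.
- **Letter.** "Upon referral, a paper copy of an instruction leaflet to health clinics will be given to the caregiver". The letter is Appendix 5.
- **General statement.** Of the home-visit staff, who are not medically trained, the section says that "if needed, they will facilitate referral to a local health facility".

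Section 4.17 describes the second sampling, two weeks after the fourth MDA round: "They will collect another heel prick blood sample and a stool sample". From the collected blood, "the nurse will measure hemoglobin and CRP concentration with an on-site reader". Section 5.02 then analyses "mean plasma CRP, blood hemoglobin and other biomarker concentration before and at two weeks after the MDA".

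**The concern.** The plan treats a raised CRP in an apparently well infant as a reason for active referral on one day and is silent on the same result a fortnight later. The test is done both times, and the nurse has the reading in hand both times. A field team following Section 6.03 literally would refer for Hb at the second visit and would have no instruction for CRP.

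What is at stake is participant safety in a sub-study of infants aged 4–11 months. The result concerned is one that the plan itself describes, in Appendix 5, as systemic inflammation and possible infection. The point does not bear on the mortality analysis.

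**Working it through.** No calculation in the plan depends on this rule, so the check sets the texts side by side.

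| Question | First visit (before MDA 4) | Second visit (day 14) |
|---|---|---|
| Blood taken? | Yes, heel-prick (4.17) | Yes, second heel-prick (4.17) |
| CRP read on site? | Yes (4.17) | Yes; the sentence is not limited to one visit (4.17), and Figure 7 lists CRP as paired, before and 14 days after |
| CRP analysed? | Yes (5.02) | Yes (5.02) |
| Referral for Hb? | Yes (6.03) | Yes (6.03) |
| Referral for CRP? | Yes (6.03) | Not stated |

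**Does other text supply the missing trigger?**

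1. *Appendix 5.* It is written for asymptomatic children. Its CRP box calls for malaria testing, assessment and, if the malaria test is negative and nothing else is found, amoxicillin for 5 days. It names no visit. But Section 6.03 hands the letter over once a referral has been made, so it guides the clinic and does not start the referral.
2. *The general statement in 6.03.* It is discretionary, gives no threshold, and describes home-visit staff, whereas a nurse takes the day-14 sample.
3. *The caregiver interview in 4.20.* It asks about symptoms since the MDA. An infant without symptoms may have none to report.

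**How many infants?** Infants affected = (infants with a day-14 reading) × (share with CRP at the threshold and Hb not at it). Figure 7 gives 1,000 for the first factor. The documents give nothing for the second, which could be anything from 0 to 100%. Each percentage point would be 1,000 × 0.01 = 10 infants. Section 4.08 adds mechanistic samples from tertiary villages without stating a number.

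**Would the added referrals disturb other analyses?** The day-14 samples are already taken when any second-visit referral is made. For later samples, follow the ages. Infants aged 4–11 months at MDA 4 (month 9) are:

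- at month 12 (+3): 7–14 months, inside the 4–14-month AMR bracket, which Section 4.07 makes descriptive at that time;
- at month 24 (+15): 19–26 months, outside both 4–14 and 49–59 months;
- at month 36 (+27): 31–38 months, again outside both.

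So the two AMR comparisons sized in Section 5.04 (4–14 months at month 36, and 49–59 months at month 24) use other children. Two smaller overlaps remain. If the paired visits are also run in tertiary villages, infants aged 9–11 months at MDA 4 would be 24–26 months at visit 9 and could enter the 24–35-month carriage sample there. Some could also be among the 12–14-month-olds measured at visit 6, when the group is 10–17 months old (+6).

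**The case against.** The best defence is that the omission is a choice. The two rules stand next to each other with different wording, and the version history records that the referral instructions for abnormal Hb or CRP were edited in version 4.0. The first-visit rule also has to settle whether a child with an abnormal value still gets the study drug, a question that does not arise at day 14. A day-14 CRP rule would also have a price. Appendix 5 leads some referred infants to amoxicillin, and if azithromycin lowers CRP, as hypothesis 13 in Section 5.01 expects, more of those courses would go to placebo villages, in clusters also used for AMR work. Finally, Section 4.20 places the two-week visit at a health facility or a central village location, so some infants will already be at a clinic.

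Part of this stands. The omission may be deliberate, the antibiotic cost is real and should be stated, and a CRP referral at day 14 is possible in practice because the Appendix 5 letter is not restricted to one visit. But the current text gives no reason, and possible is not the same as required. The trade-off is small: the first-visit CRP rule already accepts the same amoxicillin exposure, and does so before the day-14 outcome is measured. Nor can the recent dose stand in for referral. Control villages receive placebo, staff are masked, and the first-visit rule refers the infant despite dosing that day.

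A reader might infer that infants with raised CRP at day 14 would be left without care. The documents do not support that. Discretionary referral, the symptom interview and sometimes the clinic setting remain. The SOPs are not among these documents and the consent appendices for the sub-studies were not available, so either may say more.

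**Conclusion.** The gap is real but limited. Section 6.03 states a safety rule that covers CRP at one of two otherwise parallel visits, and nothing else in the available text supplies a trigger at the other. It merits correction as a participant-safety point.

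The number of infants affected is unknown. That one of the two visits lacks a CRP rule should not be read as half of the risk being uncovered, because the share with raised CRP at day 14 is not given. The conclusion assumes that the nurse has the CRP value at the second visit, as Sections 4.17 and 5.02 and Figure 7 indicate, and that no document outside this set already contains the rule. It does not assume that the omission was a mistake. Power and type 1 error for the primary mortality endpoint are untouched.

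**What to change.** In the second-visit sentence of Section 6.03, insert *or CRP* after *Hb*, so that a raised CRP in a child with no symptoms or only mild respiratory ones leads to the same active referral with transport as at the first visit. If CRP was left out on purpose, give the reason in that place instead.

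No new test, letter or referral route is needed. The costs are some additional referrals with transport and some additional five-day amoxicillin courses where the malaria test is negative and no other cause is found, possibly more of them in placebo villages. These could slightly affect the descriptive 12-month AMR sample and the two smaller overlaps shown above, so recording each second-visit referral and any antibiotic given would let the analysts describe the effect.
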